6.1.2 Population analyses

PK and safety data from this study and other future studies may be subjected to exploratory population PK-pharmacodynamic analyses. If appropriate, a detailed analysis plan will be

produced prior to any such investigations and will be reported separately. The output of these analyses may be used to influence the design of future studies.

6.1.3 Calculation or derivation of pharmacodynamic/exploratory variables (Not applicable)

6.1.4 Calculation or derivation of efficacy variables

Best overall response will be calculated as the best response recorded from date of start of study drug (taking as reference for PD the smallest measurements recorded since the treatment started) for each patient, and will be used for the summaries of objective response. Best overall response will be determined programmatically based on the RECIST criteria.

ORR is defined as the proportion of patients who have a best response of either CR or PR.

6.2 Safety evaluation

6.2.1 Calculation or derivation of safety variables

The following heart rate corrected QT intervals will be calculated: Fridericia (QTcF) and Bazett (QTcB).

The corrected QTc are calculated using:

$$QTc = \frac{QT}{RR^b}$$

(where b is 0.33 for the Fridericia correction and 0.5 for the Bazett correction).

RR = interval from the onset of one QRS complex to the onset of the next QRS complex.

6.3 Genetics as a co-variate

See [Appendix G](#).

6.4 Statistical methods and determination of sample size

6.4.1 Statistical evaluation

Full details of all data summaries and listings will be documented in a SAP, which will be prepared and finalised before clean file and datalock of the data. will produce the SAP and perform all statistical analyses. Any deviations from those analyses presented here and/or in the SAP will be detailed in the Clinical Study Report. All outputs will be produced using SAS[®] software version 9 or later.

6.4.2 Description of variables in relation to hypotheses

6.4.2.1 Primary variables

The primary objective of the study is to investigate the safety and tolerability of AZD8931. This will be done through review of:

- AEs
- Physical examination results
- Dermatological examinations
- Ophthalmological assessments
- Vital signs (BP and heart rate)
- ECG parameters
- Echocardiographic parameters
- Clinical chemistry, haematology and urinalysis.

No formal hypotheses will be associated with these variables.

6.4.2.2 Secondary variables

Pharmacokinetics

The pharmacokinetic variables to be investigated are described in Section 6.1.1. No formal hypotheses will be associated with these variables.

ECG parameters

QT, QTcB and QTcF will be reported descriptively.

6.4.2.3 Exploratory variables

Pharmacodynamic/exploratory parameters

Analysis of data for exploratory biomarkers may be carried out. Any data will be reported separately from the main study data.

Efficacy parameters

The ORR, best overall RECIST response and/or other measures of efficacy will be presented descriptively. This will include graphical presentations of the percentage change from baseline in the sum of the lengths of the RECIST target lesions for individual subjects. More details will be given in the SAP.

6.4.3 Description of analysis sets

Three patient analysis sets will be used as defined in Table 4; the safety set, the dose escalation evaluable set and the PK evaluable set. The primary analysis set will be the dose escalation evaluable set.

Table 4 **Definition of analysis sets**

Analysis set	Definition
Safety set	This population comprises all patients entered into the study who received at least one dose of AZD8931
Dose escalation evaluable set*	All patients in the safety set who have either experienced a DLT, or received at least 80% of planned doses of AZD8931 and who had all safety assessments completed during the DLT evaluation period
PK evaluable set	All patients in the safety set who have Day D1 PK data and/or have Day R14 PK data (and have received all doses during the day before Day R14)

*The SMC decide evaluability in the absence of appropriate assessments

Rules for identification of significant protocol violations will be given in the SAP. If a substantial number of patients are deemed to be protocol violators a separate ‘per-protocol’ analysis set will be determined, prior to analysis, which will exclude these patients.

6.4.4 **Methods of statistical analyses**

6.4.4.1 **Pharmacokinetic data**

The PK analysis is described in Section 6.1.1. The PK endpoints will be listed for individual subjects and summarised by dose level.

6.4.5 **Determination of sample size**

No formal sample size calculations were performed since the study follows a 3+3 dose group dose escalation design (see Section 3.1.2).

6.5 **Interim analyses (Not applicable)**

No interim analyses are planned.

6.6 **Data monitoring committee**

Working rules of the SMC are described in the SMC charter.

The SMC will comprise:

- The principal investigators of all sites
- The AstraZeneca physician
- The Medical Monitor.

In each case at least one deputy may be nominated.

On a case-by-case basis, the SMC may seek advice from further experts, including qualified representatives of AstraZeneca/

Following completion of the DLT period by ≥ 3 evaluable patients, the SMC will review all available data and decide upon dose progression. Further ‘ad-hoc’ meetings of the SMC may be convened, if required.

The safety review of data from each dose group will lead to one of 4 possible outcomes:

- Escalate to a higher dose
- Repeat dose level in further patients to obtain 6 evaluable patients at that dose level
- Stop escalation and investigate lower dose(s) – the lower dose may be intermediate between the previous dose level and current dose level
- End study.

A consensus decision must be made. The SMC may seek advice from further experts, including qualified representatives of AstraZeneca, in order to reach a consensus decision. All decisions will be documented, and distributed to all SMC members.

No formal statistical analyses will be performed in the safety review.

Based on emerging data, including PK and/or safety data and/or pre-clinical data, the SMC can consider alternative schedules, including once-daily dosing, in consultation with AstraZeneca and

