2. STUDY OBJECTIVES

2.1 Primary objective

The primary objective of this study is to explore the safety and tolerability of multiple ascending doses (MAD) of AZD8931 in patients with advanced solid malignancies, by evaluation of AEs, laboratory findings, physical examinations, vital signs, cardiac monitoring, and ophthalmological assessments.

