3.1.2 Criteria to conduct dose escalation

The DLT evaluation period starts from the first administration of AZD8931 and continues until the completion of all assessments prior to cycle 2. For patients who continue beyond cycle 1, the DLT evaluation period ends following the completion of pre-dose assessments on the first day of cycle 2 (ie R1 cycle 2). For those patients who do not proceed beyond cycle 1 the DLT evaluation period ends following the completion of all assessments on the last day of cycle 1. Following cycle 1, subsequent treatment cycles are continuous. Dose reductions are not permitted during the DLT evaluation period, except following a DLT. If dosing of AZD8931 needs to be interrupted due to intolerable toxicities, then the DLT evaluation period may extend by the appropriate duration. Dose omissions for any other reason must not extend the DLT evaluation period. Evaluability of such patients will depend on meeting the description of analysis sets as described in Table 4 (Section 6.4.3). The cohorts may remain open until a maximum of 6 patients within the cohort have been defined as evaluable and thereafter further recruitment into that cohort will be closed pending a decision from the SMC.

Prior to each dose escalation, the SMC (see Section 6.6) will meet to review the available safety, tolerability (including AEs, laboratory assessments, ophthalmic assessments, physical examinations, vital signs, cardiac monitoring parameters) and PK data. The dose escalation decision will be documented and the minutes will be distributed to each site.

[figure not shown]
Throughout the study, dose escalation decisions will be based on a minimum of 3 and a maximum of 6 evaluable patients per dose cohort (see 'dose escalation evaluable set' described in Table 4). If a patient has received less than 80% of the defined dose and this is due to toxicity, a discussion will take place between AstraZeneca and the investigator to determine if this is a DLT. Replacement patients will enrol until the minimum required number of evaluable patients is available for assessments – see Section 3.4.4 for information on replacement of patients. Reasons for patient withdrawal will be given due consideration when enrolling replacement patients.

The SMC will review the data from each of the patients who completed the DLT evaluation period and decide if dose escalation is appropriate according to the following criteria:

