3.4.4 Method of assigning subjects to treatment groups

Informed consent will be obtained at screening and each patient will be identified with a unique screening number starting with E# (incorporating centre identification). This number will be retained regardless of whether they subsequently fulfil the eligibility criteria.

Patients will be assigned patient numbers strictly sequentially as patients become eligible for inclusion. If a patient discontinues from the study the patient number will not be re-used and the patient will not be allowed to re-enter the study.

Patients may be replaced if they are withdrawn without meeting all the criteria for a DLT (see Section 3.1.2), or withdrawn due to a DLT that is attributed to taking confounding medications (see Section 3.1.5), or if they are enrolled in error (see Section 3.3.5.4), or if they are non-evaluable (see Section 6.4.3).

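### The primary analysis set for a safety objective is the dose escalation evaluable set, so toxicity short of a DLT that stops or cuts dosing can fall outside the primary safety summaries

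*Protocol*

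**What the plan says.** All references are to the Protocol.

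- **Objective and variables.** Section 2.1: "The primary objective of this study is to explore the safety and tolerability of multiple ascending doses (MAD) of AZD8931". Section 6.4.2.1 repeats this ("The primary objective of the study is to investigate the safety and tolerability of AZD8931") and lists only safety variables: adverse events, physical, skin and eye examinations, vital signs, ECG, echocardiography and laboratory tests. Identifying the MTD from DLTs is a secondary objective (section 2.2).
- **Primary set.** Section 6.4.3: "The primary analysis set will be the dose escalation evaluable set".
- **Entry to that set (Table 4).** The patient either had a DLT or "received at least 80% of planned doses of AZD8931 and who had all safety assessments completed during the DLT evaluation period". A footnote adds: "The SMC decide evaluability in the absence of appropriate assessments".
- **Safety set (Table 4).** "This population comprises all patients entered into the study who received at least one dose of AZD8931". It is one of three sets that section 6.4.3 says will be used, but nothing in section 6.4 ties it to a variable.
- **Replacement.** Section 3.4.4 allows replacement of patients "withdrawn without meeting all the criteria for a DLT" and of non-evaluable patients generally. Section 3.1.5 replaces a patient whose toxicity the SMC rules not to be a DLT. Section 3.4.3 makes a patient non-evaluable if the dose is reduced during the DLT evaluation period without a DLT.
- **Low dosing for toxicity.** Section 3.1.2: "If a patient has received less than 80% of the defined dose and this is due to toxicity, a discussion will take place" between the sponsor and the investigator, to settle whether it is a DLT.

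**The concern.** The evaluable set is built for the escalation decision. There it makes sense to count only patients who either had a DLT or were exposed and observed for long enough to be called free of one. For a description of safety and tolerability, the same rule selects patients partly on the outcome: without a DLT, a patient qualifies by having taken most of the planned doses. Someone who stops in the first cycle because of troublesome toxicity that does not meet the DLT definition is informative about tolerability, yet can be outside the set named as primary, with a replacement patient inside it.

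At stake is how the primary objective is reported at each dose level, in particular early stopping and dose cuts for toxicity below the DLT threshold. The escalation rule and the MTD are not in question, since the evaluable set is the right one for them.

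**Working it through.** **1. The plan's own size.** Section 3.1.1 gives about 5 dose groups of 3 to 6 evaluable patients: 5 × 3 = 15 to 5 × 6 = 30. This reproduces the stated maximum of about 30 evaluable patients. There is no power calculation to check (section 6.4.5).

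**2. The dosing threshold.** Section 3.1.1 plans one single dose and then 21 days of twice-daily dosing.
- Planned doses: 1 + 2 × 21 = 43
- 80% of 43 = 34.4, so at least 35 doses are needed
- Doses that may be missed: 43 − 35 = 8, about 4 days
- Twice-daily days needed if none is missed: (35 − 1) / 2 = 17

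A patient without a DLT who stops before completing about day R17, or who misses 9 or more doses, is outside the primary set. These counts hold for the twice-daily schedule without extension of the period.

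**3. A route by which toxicity can lead out of the set.** Under section 3.1.5, rash is a DLT only if it stays at grade 3 or higher for 5 days or longer despite optimal treatment. Appendix I suspends dosing once rash reaches grade 3. A shorter grade 3 rash can thus cost doses without meeting the rash criterion.

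**4. How many treated patients could be left out.** The protocol gives no non-evaluable share, so d below is an assumption. Treated = 30 / (1 − d), rounded up.

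| Assumed d | Treated | Outside the primary set |
|---|---|---|
| 10% | 30 / 0.9 → 34 | 4 |
| 20% | 30 / 0.8 → 38 | 8 |
| 30% | 30 / 0.7 → 43 | 13 |

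**5. Effect on an adverse event rate.** Assume 20% of the 30 evaluable patients have the event (30 × 0.20 = 6) and a fraction p of those left out do. The primary set shows 20% in every case. The all-treated rate is (6 + left out × p) / treated.

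| Treated (left out) | p = 20% | p = 50% | p = 80% |
|---|---|---|---|
| 34 (4) | 20% | 8.0/34 = 23.5% | 9.2/34 = 27.1% |
| 38 (8) | 20% | 10.0/38 = 26.3% | 12.4/38 = 32.6% |
| 43 (13) | 20% | 12.5/43 = 29.1% | 16.4/43 = 38.1% |

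All event rates here are assumptions. With equal rates (p = 20%) there is no bias.

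**The case against.** The strongest reply is that the safety set exists, that section 6.4.3 says it will be used, and that section 6.4.1 leaves full details of the summaries to the SAP. Matching tables to sets is ordinary SAP business. That would settle the matter if the protocol were silent, but it names the primary set itself, and section 6.4.3 defers only the rules for protocol violations. A SAP that used the safety set for the primary safety tables would depart from the protocol sentence.

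The second reply is that the excluded group is small. Much of this stands:
- Low dosing caused by toxicity is discussed and may be classed as a DLT, and interruption for intolerable toxicity may extend the evaluation period (section 3.1.2).
- The DLT definition takes in other grade 3 or higher toxicity that the investigator judges clinically significant and related (section 3.1.5), so most severe drug-related events keep the patient in the set.
- The SMC can decide evaluability when assessments are missing (Table 4 footnote).
- Section 3.1.2 bars dose reduction in the evaluation period except after a DLT, while section 3.4.3 provides for reduction without one. These two passages need to be reconciled; until then the reduction route is uncertain.

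These safeguards narrow the group. They are largely case-by-case judgements, so they do not close it.

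A reader might also infer that replaced patients' data are discarded. They are not: such patients meet the safety set definition, adverse events are collected until 30 days after the last dose (section 4.7.1.2), and the SMC reviews all available data (section 6.6).

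**Conclusion.** The sentence in section 6.4.3 does not fit the primary objective. It makes the declared primary safety analysis depend partly on patients having tolerated the drug, and tolerability failures short of a DLT can be understated. With 30 evaluable patients and an assumed non-evaluable share of 10% to 30%, the primary set leaves out 4 to 13 of 34 to 43 treated patients. The protocol supplies no rate with which to narrow that range.

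Three stronger readings are not supported:
- **Any missed dose excludes a patient.** Up to 8 of 43 doses may be missed.
- **The primary set shows no stopping for toxicity.** Patients with a DLT who stop early remain in it. A zero arises only for an outcome defined by the exclusion rule itself, so it says nothing about adverse event rates in general.
- **Adverse event rates are certain to be understated.** That direction is likely but not established. Patients also become non-evaluable through disease progression, withdrawal, enrolment error or prohibited medication, none of which implies more toxicity.

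No formal hypothesis is attached to the primary variables, so what is affected is description and reporting, not a test or an escalation decision.

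**What to change.** Replace the sentence on the primary set in section 6.4.3 with wording to this effect:

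> All safety and tolerability variables are summarised by dose level in the safety set. The dose escalation evaluable set is primary only for the DLT rate and the MTD. The PK evaluable set is used for PK. Any safety table in the dose escalation evaluable set is supportive.

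The SAP and table shells should follow the same assignment. The cost is a short protocol amendment and a check of the shells. It needs no further patients or data and no change to any escalation or treatment rule.

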The non-validated PK results showed that AZD8931 is orally bioavailable over the dose range 2.5 mg to 200 mg. Absorption was moderately rapid with time to reach maximum plasma concentration (t_{max}) occurring in most subjects at 1.5 or 2 hours after the dose (range 0.5 to 4 hours). After reaching the maximum plasma concentration (C_{max}), plasma concentrations declined biphasically. A terminal phase became apparent from about 24 hours after the dose,

when the plasma concentrations had fallen to around 6% of the peak values. The mean terminal elimination half-life ($t_{1/2}$) across the dose range was 12.1 hours (range 7.6 to 16.6 hours).

Based on the above data, it was determined that twice-daily administration should be employed in the current study to avoid excessive fluctuations between steady state (ss) C_{max} ($C_{ss_{max}}$) and minimum plasma concentration ($C_{ss_{min}}$). It is predicted that twice-daily dosing will lead to accumulation of study drug at about 30%, with a 5-fold fluctuation between $C_{ss_{min}}$ and $C_{ss_{max}}$.

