3.4.2 Doses and treatment regimens

3.4.2.1 AZD8931 dosing

AZD8931 tablets will be taken orally twice daily (except for the single dose on D1), with the doses being taken approximately 12 hours apart. The AZD8931 tablets should be taken with a glass of water (approximately 150 mL) at approximately the same time each day. The effect of food on the absorption of AZD8931 has not been established. Therefore it is requested that AZD8931 be taken at least 2 hours after a meal and that no food is consumed until 2 hours after the tablets are taken. There is no restriction on the consumption of water.

The initial dose level will be 40 mg. See also Section [3.1.2](#) for more details on dose escalation.

Day 1 of a subsequent cycle is the day after the last day of the previous cycle (R21) i.e. AZD8931 dosing is continuous twice daily (except if there is a dose interruption due to toxicity).

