3.4.3 Dose adjustment of AZD8931

Intra-patient dose adjustment of AZD8931 may be permitted according to the criteria detailed below and only after discussion and agreement of individual patient situations between the investigator, the medical monitor and the sponsor. During the study, the dose of AZD8931 may only be reduced by one dose level for an individual patient if required.

- For all patients who experience a DLT or an unacceptable toxicity, if the toxicity does not resolve to CTCAE \leq grade 1 or baseline (pre-study) after 21 days of onset, then the patients must be discontinued from the study
- If a DLT or unacceptable toxicity resolves or reverts to CTCAE \leq grade 1 or baseline levels within 21 days of onset and the patient is showing or, in the investigators opinion may show clinical benefit, treatment with AZD8931 may be restarted at a preceding, lower dose level that has been defined as tolerated

The dose of AZD8931 may only be reduced by 1 dose level in any given patient. If this dose reduction occurs during the DLT evaluation period the patient will no longer be defined as evaluable for the presence of DLT, unless they have already experienced a DLT (see Section 3.1.2).

All dose modifications and interruptions (including any missed doses due to AEs), and the reasons for the dose modifications/interruptions are to be recorded in the CRF.

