6. PHARMACOKINETIC, PHARMACODYNAMIC, SAFETY, GENETIC AND STATISTICAL METHODOLOGY

6.1 Pharmacokinetic / pharmacodynamic evaluation

6.1.1 Calculation or derivation of pharmacokinetic variables

The PK analyses will be performed by Clinical Pharmacology and DMPK AstraZeneca.

PK parameters to be calculated are:-

- Single dose plasma PK
 - AUC from time zero to 12 hours (AUC_{0-12}), 24 hours (AUC_{0-24}), time t (AUC_{0-t}) and infinity (AUC) after dosing, C_{max} , t_{max} , $t_{1/2}$, total apparent drug clearance (CL/F), apparent volume of distribution at (V/F)
- Multiple dose plasma PK
 - time to ss and assessment of any accumulation of AZD8931, including AUC_{SS0-12} , C_{SSmax} , time to reach maximum plasma concentration at steady state (t_{SSmax}), CL_{SS}/F , C_{SSmin} , accumulation ratio (R_{AC}) and linearity factor

Other PK parameters may be determined if deemed appropriate.

Minimum plasma concentration (C_{min}), C_{max} and t_{max} (and C_{SSmin} , C_{SSmax} and t_{SSmax}) will be determined by visual inspection of the plasma concentration time profile. The area under the plasma concentration time curve from time zero to 12 and 24 hours after dosing, AUC_{0-12} and AUC_{0-24} , respectively, and from zero to the time of the last quantifiable plasma concentration, AUC_{0-t} , will be calculated using the linear trapezoidal rule (linear/log interpolation). The $t_{1/2}$ will be calculated from the equation $\ln(2)/\lambda_z$ (where the rate constant of the slowest disposition phase [λ_z] will be calculated by log linear regression of the terminal portion of the concentration time profile where there are sufficient data [ie, the terminal phase is followed for at least $3 \times t_{1/2}$]). The AUC will be derived by using λ_z to extrapolate AUC_{0-t} to infinity. CL/F and V_{SS}/F will be estimated by dividing the dose by the AUC and multiplying mean residence time by CL/F, respectively. Linearity factor will be determined by dividing AUC_{SS0-12} by AUC after the single dose and R_{AC} will be determined by dividing AUC_{SS0-12} by AUC_{0-12} after the single dose.

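### The Day R14 to Day 1 exposure ratios are not corrected for dose, so a patient restarted one level lower before R14 shows a falsely low accumulation ratio and linearity factor

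*Protocol*

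**What the plan says.** **PK set.** Table 4 (protocol Section 6.4.3) admits safety-set patients who have Day D1 PK data, Day R14 PK data, or both. The only dosing condition attached to R14 is "and have received all doses during the day before Day R14". Nothing is required of the dose level, or of dosing from R1 to R12.

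**Derivation.** Section 6.1.1 fixes both ratios. For the first: "Linearity factor will be determined by dividing AUC_{SS0-12} by AUC after the single dose". R_AC "will be determined by dividing AUC_{SS0-12} by AUC_{0-12} after the single dose". Neither formula contains the dose.

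**Reporting.** Section 6.4.4.1 states: "The PK endpoints will be listed for individual subjects and summarised by dose level". It does not say whether this is the assigned level or the level actually taken.

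**Dose changes.** Section 3.1.2 rules out reductions in the DLT evaluation period except after a DLT. Under Section 3.4.3, if the toxicity resolves and benefit is seen or thought possible, "treatment with AZD8931 may be restarted at a preceding, lower dose level that has been defined as tolerated". The reduction is limited to one level. Section 3.4.3 says what a reduction does to DLT evaluability but nothing about the PK set. Section 3.3.5.4, by contrast, explicitly removes wrongly enrolled patients from the PK evaluation.

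**The concern.** Both ratios compare a patient with himself or herself, and they can be read as accumulation and time-linearity only if numerator and denominator come from the same dose. The protocol permits a route by which they do not: a DLT, recovery, a restart one level lower, and an R14 profile after both R13 doses were taken. Such a patient meets Table 4 and enters R_AC and the linearity factor with a ratio lowered by the dose change alone.

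Multiple-dose PK is a secondary objective (Section 2.2). A linearity factor well below 1 would normally suggest that clearance rises on repeat dosing, when here it would only record the reduction. The error can occur only at levels where DLTs occur, which are the levels around the MTD, and cohorts hold only 3 to 6 evaluable patients.

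**Working it through.** **Inputs**
- Predicted accumulation on twice-daily dosing: about 30%, so R_AC about 1.30 (Section 1.1.2).
- Dosing interval 12 h (Section 3.4.2.1: "with the doses being taken approximately 12 hours apart").
- Concentration about 6% of peak at 24 h, t_max mostly 1.5 to 2 h, terminal half-life 12.1 h on average with a range of 7.6 to 16.6 h (Section 1.1.2; non-validated, healthy volunteers).
- Dose increments never more than a doubling (Section 3.2.1), so one level down multiplies the dose by f, with f at least 0.5.

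**1. Reproduce the protocol's 30%.** With r = 0.5^(12/t½), accumulation is R = 1/(1 − r).
- A fall to 6% of peak over the 22.25 h from t_max 1.75 h to 24 h gives an effective half-life of ln 2 × 22.25 / ln(1/0.06) = 5.48 h, and R = 1.28. Over t_max 1.5 to 2 h, R is 1.29 to 1.27. This matches about 30%.
- R = 1.30 exactly gives r = 1 − 1/1.30 = 0.231, a half-life of 5.67 h.
- The terminal half-life alone would give R = 2.01 at 12.1 h and 2.54 at 16.6 h, so it does not govern accumulation in the protocol's own prediction.

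**2. Effect of a dose reduction on the patient.** With dose-proportional, time-invariant kinetics and steady state at the reduced dose, R_AC = 1.30 × f and the linearity factor = f.

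| f | R_AC | Linearity factor |
|---|---|---|
| 1 (no change) | 1.30 | 1.00 |
| 0.75 | 0.98 | 0.75 |
| 0.5 (one halving) | 0.65 | 0.50 |

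**3. Effect on the cohort mean**, one halved patient summarised under the assigned dose:
- n = 6: R_AC (5 × 1.30 + 0.65)/6 = 1.19; linearity factor (5 × 1.0 + 0.5)/6 = 0.92.
- n = 3: R_AC (2 × 1.30 + 0.65)/3 = 1.08; linearity factor (2 × 1.0 + 0.5)/3 = 0.83.

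A DLT in one patient leads to recruitment towards six (Section 3.1.2), so n = 6 is the more likely case.

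**4. Interruption without a dose change, for comparison.** Take the extreme case: complete washout, then only the two R13 doses. The R14 dose is then the third, and its 12 h AUC is 1 − r³ of the steady-state value.
- At 5.67 h: 1 − 0.231³ = 98.8%, so R_AC reads 1.28 against 1.30.
- A biexponential curve with the terminal half-life fixed at 12.1 h, fitted to the protocol's features (fit: 5.9% at 24 h, t_max 1.85 h, R 1.34), gives about 95%.
- Only if the terminal half-life governed all exposure would it be 87% (12.1 h) or 78% (16.6 h), which step 1 does not support.

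**The case against.** The best reply is that the route is narrow. Before R14 it needs a DLT, resolution to grade 1 or baseline, actual or possible benefit, agreement between the investigator, medical monitor and sponsor, a preceding level already declared tolerated, and a restart in time for the R13 doses. The first cohort has no preceding level. Some DLTs are unlikely to be found and resolved by then: scheduled echocardiography and full eye examinations fall at R21. Dose changes go in the CRF, PK endpoints are listed per patient, no hypothesis rests on these variables, and Section 6.4.1 leaves the detail of summaries to the SAP.

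All of this stands as a limit on frequency and harm. It does not remove the defect. The formulas are fixed in the protocol itself. The protocol-violation rules left to the SAP need not catch a reduction that the protocol permits. Membership of the PK set does not oblige every parameter to be summarised, but no rule keeps this one out. The cohort figures do depend on grouping by assigned dose, which the protocol leaves open.

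Three stronger readings are tempting and not supported:
- A reader might infer that patients who resume after an interruption also distort the ratios, since one day covers only about two terminal half-lives. On the protocol's own PK figures the shortfall after a full washout is about 1 to 5%.
- For the same reason, a reader might want several dose-complete days before R14, for example 5 × 16.6 h = 83 h. That rests on a half-life that would give accumulation of 2.5, not 1.3, and would discard scarce profiles for little gain.
- A reader might infer that escalation decisions are affected, because Section 3.1.2 refers to exposure above prediction. It does not say which exposure measure is meant, so this cannot be shown.

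**Conclusion.** The point holds for dose reduction. Applied as written, Table 4 and Section 6.1.1 give a patient reduced by one halving an R_AC of about 0.65 instead of 1.30 and a linearity factor of 0.5 instead of 1.0. Under assigned-dose grouping, one such patient moves mean R_AC to about 1.19 (n = 6) or 1.08 (n = 3).

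These figures assume dose-proportional and time-invariant kinetics, the predicted 30% accumulation, and a full halving. Smaller steps give proportionally smaller errors. The documents give no frequency; the conditions make the case infrequent, and it cannot arise at 40 mg unless a lower level is opened. It deserves correction because one patient carries weight in cohorts this small and the correction is nearly free. It does not threaten the safety objective or the MTD rule.

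**What to change.** In Section 6.1.1, divide each AUC by the dose that produced it before forming R_AC and the linearity factor. The alternative, in Section 6.1.1 or Table 4, is to compute the two ratios only when the R14 dose level equals the Day 1 dose level and to list the remaining patients. Dose normalisation has the advantage that it keeps the profiles and does not selectively drop patients who had a DLT.

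In Section 6.4.4.1, state that R14 PK is summarised by the dose actually taken.

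The cost is one or two lines of text. No new data are needed, because dose modifications are already recorded in the CRF. Under the equal-dose option, a few ratios move from summary to listing.
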